Primary Endpoint	
Acute Pain: Silverman Integrated Analgesic Assessment (SIA) score (a composite of pain and opioid usage) at 10 days post-surgery in participants who are genetically or pheno-converted CYP2D6 IM or PM
 
Chronic Pain: Pain control, defined as change in the composite pain intensity score from baseline to 3-months in participants who are genetically or pheno-converted CYP2D6 IM or PM
 
Depression: Depression symptom control, defined as change in PROMIS depression 8A scores from baseline to 3-months in genetically or pheno-converted CYP2D6 UM/PM or CYP2C19 UM/RM/PM

Secondary Endpoints	
Acute Pain:
 
 • Pain intensity at 10 days post-surgery • Opioid usage at 10 days post-surgery • Prescription pain medication misuse score 3 months post-surgery • Mobility score 1-month post-surgery • Opioid persistence 6 months post-surgery 
Chronic Pain:
 
 • Pain reduction magnitude at 3-month follow-up, relative to baseline • Achievement of clinically significant pain reduction (30%) by 3-month follow-up, relative to baseline • Prescription pain medication misuse score at 3-month follow-up 
Depression:
 
 • Change in PHQ-8 scores between baseline and 3 months • Achieve 50% reduction in PHQ-8 scores at 3 months, relative to baseline • Medication side effects severity burden at 3 months • Participant medication adherence at 3 months • Achieve remission at 6 months defined as PROMIS depression score ≤ 16 • Achieve remission at 6 months, defined as PHQ-8 score ≤ 4 
All Trials:
 
 • Overall well-being at 6 months in all randomized participants • Concordance between metabolizer phenotype and prescribed medication • Sub-domains of the PROMIS 43 survey: pain interference, physical function, sleep disturbance, social role and activities functioning, fatigue, anxiety, and depression at 6-month follow-up
Statistical Analyses	
Acute Pain:
 
 • The effect of genotype guided opioid therapy on pain control will be determined by comparing the 10-day post-surgery SIA scores of the Intervention arm participant with CYP2D6 IM or PM phenotypes to the 10-day post-surgery SIA scores of the Control arm participant with CYP2D6 IM or PM phenotypes using a two-sided t-test or a two-sided Mann Whitney

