- test, as appropriate, with a two-sided type 1 error rate of 0.049
- Similarly, the effect of genotype guided opioid therapy on all secondary endpoints will be compared between the Intervention arm CYP2D6 IM or PM phenotype and the Control arm CYP2D6 IM or PM phenotype using a two-sided t-test or a two-sided Mann Whitney test
- Additional analyses will include time trends in primary and secondary endpoints, subset analyses, covariate adjustments, and exploratory healthcare utilization and cost effectiveness analyses

Chronic Pain:

- The effect of genotype guided opioid therapy on pain control will be determined by comparing the change in baseline to 3-month follow-up composite pain scores of the Intervention arm participants with CYP2D6 IM or PM phenotypes to the change in baseline to 3-month follow-up composite pain scores of the Control arm participants with CYP2D6 IM or PM phenotypes using a two-sided t-test with type 1 error rate of 0.049
- Similarly, the effect of genotype guided opioid therapy on all chronic pain secondary endpoints will be compared between the Intervention arm CYP2D6 IM or PM subgroup and the Control arm CYP2D6 IM or PM subgroup using either a two-sided t-test or a test of two proportions, as appropriate.
- Additional analyses will include time trends in primary and secondary endpoints, subset analyses, covariate adjustments, and exploratory healthcare utilization and cost effectiveness analyses

Depression:

- The effect of genotype guided antidepressant therapy on depression symptoms will be determined by comparing the 3-month follow-up composite depression scores of the Intervention arm participant subgroup with CYP2D6 UM or PM or CYP2C19 UM, RM, or PM phenotypes to the 3-month follow-up composite depression scores of the Control arm participant subgroup with CYP2D6 UM or PM or CYP2C19 UM, RM, or PM phenotypes using a two-sided t-test with type 1 error rate of 0.049
- Similarly, the effect of genotype guided antidepressant therapy on all depression secondary endpoints will be compared between the Intervention arm CYP2D6 or CYP2C19 UM, RM or PM subgroup and the Control arm CYP2D6 or CYP2C19 UM, RM, or PM subgroup using either a two-sided t-test, a two-sided Mann Whitney test, or a test of two proportions, as appropriate.
- Additional analyses will include time trends in primary and secondary endpoints, subset analyses, covariate adjustments, and exploratory healthcare utilization and cost effectiveness analyses

All Trials:

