3. ENDPOINTS

3.1 Primary Endpoint(s)

Acute pain: The primary endpoint for the acute pain study is the SIA score, a composite of pain and opioid usage, at 10 days post-surgical procedure. See Appendix A for the SIA score rationale.

Chronic pain: The primary endpoint for the chronic pain study is change in composite pain intensity score, assessed using the PROMIS pain intensity survey, from baseline to 3 months post return of genetic testing results to the provider.

Depression: The primary endpoint for the depression study is change in depression score, assessed using the PROMIS Emotional Distress - Depression 8b survey (adults) or PROMIS pediatric depressive symptoms (pediatric), from baseline to 3 months post return of genetic testing results to provider.

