In prior studies of depression, the difference between study arms in PROMIS 8a T-scores was -6.7 with a SD of 10, for a standardized effect size of -.67. For the purposes of power analysis, a 4-point change is considered the minimally important difference representing a response to therapy that is congruent with the predicted CYP enzyme phenotype compared to the response to therapy which

conflicts with the phenotype.

Preliminary data from published studies indicate the proportion of participants with an actionable phenotype (CYP2C19 PM, RM, UM or CYP2D6 PM or UM, or pheno-converted CYP2D6 PM or UM) will be 40%. However, due to the distribution of study-related antidepressants in primary care and behavioral health settings, an estimated 67% of the participants with an actionable phenotype are anticipated to also have a study-related dosing or drug selection intervention. In other words, the analytic group of CYP2DC UM, PM, or CYP2C19 UM, RM, or PM phenotypes will represent a mixture of participants that may have a clinically meaningful change in depression due to being prescribed a study-relevant antidepressant and participants that may have changes in depression typical of the standard of care arm since they are not being prescribed a study-relevant antidepressant. In accounting for this population mixture, we incorporated a dilution factor of 67% into the clinically meaningful effect size projection and assume the effective difference of 0.28, representing a 2.8-point change to the T-score. We will need 542 modified intent to treat participants, 271 in each arm, to detect a standardized effect size of 0.28 with 90% power. After adjusting for the subset anticipated to have an actionable phenotype (i.e. 40%), 678 participants completing all assessments, per group, are required to achieve 90% power in the mITT analysis (1356 total). After accounting for 90% retention, 754 participants from the intervention arm and 754 participants from control arm (1508 total) are required to achieve 90% power for a two-sided two-sample t-test. Factoring in variability for the on the mITT proportion of the randomized population (40-60%), 1006-1508 randomized subjects would be needed to achieve 90% power in the mITT analysis.

Table 9. Sample size calculations

Sample size calculations for each trial, assuming an alpha of 0.049 to allow for one interim analysis

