participants, we will conduct a subset analysis comparing change in depression T-scores from baseline to 3-month follow-up in the Intervention group subset with either CYP2D6 PM or UM or CYP2C19 PM, RM or UM phenotypes to the Control group subset with CYP2D6 PM or UM or CYP2C19 PM, RM, or UM phenotypes. Participants that have other CYP2D6 or CYP2C19 phenotypes will not be included. Pediatric depression T-scores will be transformed to the adult scale using a published crosswalk for a combined analysis. The baseline to 3-month change in depression T-scores of the Intervention CYP2D6 PM/UM or CYP2C19 PM/RM/UM group will be compared to the baseline to 3-month change in depression T-scores of the Control CYP2D6 PM/UM or CYP2C19 PM/RM/UM subgroup using a two-sided two-sample t-test with a type 1 error of 0.049. This primary analysis will be conducted according to a modified intent-to-treat design, with participants analyzed and endpoints attributed according to the treatment arm to which the participants were randomized, regardless of subsequent crossover or post-randomization medical care.

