11.2 Data Element Definitions

Clinically significant pain reduction: Whether or not the pain reduction score is ≤ 0.7 . If the pain reduction score is ≤ 0.7 , clinically significant pain reduction is achieved, if pain reduction scores is > 0.7 , clinically significant pain reduction is not achieved.

Depression symptom control: The change in the PROMIS Emotional Distress - Depression 8b or PROIMIS pediatric Depression 8a survey depression score from baseline to time t.

Depression remission: A. Whether or not the summed raw PROMIS emotional distress depression 8b survey responses are ≤ 16 , which is equivalent to the participant responding “rarely” or “never” to most or all of the PROMIS emotional distress - depression 8b survey questions. B. Whether or not the PHQ-8 scores are ≤ 4 , which is equivalent to depression severity being none-mild.

Depression (PHQ-8) score: The sum of the responses to the PHQ-8 survey, range from 0 to 24.

Depression (T) score: The T-score converted summed responses to the PROMIS emotional distress depression 8b survey. The T-score conversion is centered around 50 with standard deviation of 10.

Depression severity: The depression score converted to depression severity (none, mild, moderate, severe) based on the scoring guide for the PROMIS emotional distress depression 8b survey.

Medication adherence: The scored responses to the Voils Medication Adherence survey.

Medication concordance: Whether or not the medication the participant is prescribed after the intervention is concordant with the participants CYP2D6 and, for the depression trial, CYP2C19 phenotype.

Medication side effects severity burden: (Depression only) The sum of the scored severity (none = 0, mild = 1, moderate = 2, severe = 3) for common SSRI side effects.

Opioid misuse score: The T-score converted summed responses to the PROMIS prescription medication misuse 7a survey. The T-score conversion is centered around 50 with standard deviation of 10.

Opioid persistence: Defined as ≥ 1 opioid prescription refill between 90 days and 180 days after the surgical procedure.

Opioid usage: The average daily morphine equivalents in mg (MED) in past 7 days. MEDs will be calculated using data from the opioid usage survey.

Overall well-being: Defined as the T-score converted summed responses to the PROMIS 43/PROMIS 37 pediatrics survey. The T-score conversion is centered around 50 with standard deviation of 10.

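### The synopsis states the depression primary t-test on 3-month scores, while every definition of the endpoint and section 10.4 use change from baseline; 10.1 does not say which of the two its SD of 10 describes

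*Combined protocol and SAP*

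**What the plan says.** The depression bullet in the synopsis (section 1, Statistical Analyses) sets the primary test as "comparing the 3-month follow-up composite depression scores of the Intervention arm participant subgroup" against the same scores in the control subgroup, by two-sided t-test at a type 1 error of 0.049.

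Four other places define the primary comparison on change:

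- Synopsis, Primary Endpoint row: "Depression symptom control, defined as change in PROMIS depression 8A scores from baseline to 3-months".
- Section 3.1: "The primary endpoint for the depression study is change in depression score", measured from baseline to 3 months after results are returned.
- Section 10.4: "comparing change in depression T-scores from baseline to 3-month follow-up in the Intervention group subset", again by two-sided t-test at 0.049, with no baseline covariate.
- Section 11.2, definition of depression symptom control: "The change in the PROMIS Emotional Distress - Depression 8b or PROIMIS pediatric Depression 8a survey depression score from baseline to time t".

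In section 10.1, the prior evidence is that "the difference between study arms in PROMIS 8a T-scores was -6.7 with a SD of 10". The trial is then sized on a standardised effect of 0.28, equated to 2.8 T-score points, with 271 analysed per arm and 90% power. Section 10.1 does not say whether the SD of 10 is for a single score or for the change, and gives no correlation between baseline and 3 months.

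**The concern.** The bullet gives the same test at the same alpha as 10.4, but on a different variable. It is hard to read as shorthand, because the chronic pain bullet in the same row does specify change from baseline.

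Without a baseline covariate the two variables give different tests. Follow-up scores ignore any baseline difference between arms, and change scores subtract it in full. Section 10.6 itself warns that baseline characteristics may differ between arms within the actionable-phenotype subgroup, but it adjusts for this only in exploratory models. The trial is also open label, so the primary test should be stated identically wherever it appears.

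The sample size leaves a second gap. A standardised effect of 0.28 fits whichever variable has an SD of 10, so the stated power cannot be tied to the 10.4 test without more information.

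**Working it through.** **Inputs.** Two-sided alpha 0.049, 90% power, difference 2.8 points, SD 10 and 271 per arm (all section 10.1). The correlation ρ between baseline and 3-month T-scores is not in the documents; 0.3 to 0.7 is assumed. Equal SDs at the two times are also assumed. Power is for a two-sample t-test (noncentral t).

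**Step 1: the plan's own figure.** An effect of 0.28 needs 270.4 per arm, so 271 (542 in total), with 90.1% power. Then 271/0.40 = 677.5, so 678 per arm, and 678/0.90 = 753.3, so 754 per arm (1508 in total). The plan's numbers reproduce, and they do so for any variable with an SD of 10.

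**Step 2: how the two estimates differ.** Write F for the 3-month mean, B for the baseline mean, and I and C for the arms. Then (F_I − F_C) − [(F_I − B_I) − (F_C − B_C)] = B_I − B_C. If the baseline SD is 10 (assumption), this difference has a standard error of 10 × √(2/271) = 0.86 points, against a target of 2.8. Its expectation is zero under randomisation, but in a single trial it can move the p-value.

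**Step 3: power if 10 is the SD of a single score.** The follow-up test has d = 0.28 and 90.1% power at any ρ. For change, SD = 10√(2(1 − ρ)). For the 3-month score adjusted for baseline, the residual SD is 10√(1 − ρ²).

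| ρ | SD of change | Change test (10.4) | Follow-up test | Baseline-adjusted |
|---|---|---|---|---|
| 0.3 | 11.83 | 78.3% | 90.1% | 92.5% |
| 0.4 | 10.95 | 84.2% | 90.1% | 94.3% |
| 0.5 | 10.00 | 90.1% | 90.1% | 96.3% |
| 0.6 | 8.94 | 95.2% | 90.1% | 98.2% |
| 0.7 | 7.75 | 98.7% | 90.1% | 99.5% |

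**Step 4: power if 10 is the SD of the change.** The 10.4 test has 90.1% at any ρ. The score SD is 10/√(2(1 − ρ)), and the baseline-adjusted residual SD is 10√((1 + ρ)/2).

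| ρ | SD of score | Change test (10.4) | Follow-up test | Baseline-adjusted |
|---|---|---|---|---|
| 0.3 | 8.45 | 90.1% | 97.0% | 98.1% |
| 0.4 | 9.13 | 90.1% | 94.5% | 97.3% |
| 0.5 | 10.00 | 90.1% | 90.1% | 96.3% |
| 0.6 | 11.18 | 90.1% | 82.7% | 95.2% |
| 0.7 | 12.91 | 90.1% | 70.9% | 94.1% |

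**Step 5: sensitivity to equal SDs.** In general the two unadjusted tests have equal power at ρ = SD_baseline/(2 × SD_follow-up). That is 0.5 only when the SDs are equal. With a follow-up SD of 10 and a baseline SD of 8 it is 0.40. At ρ = 0.3 the SD of change is then √(64 + 100 − 2 × 0.3 × 80) = 10.77, and the change test has 85% power, not 78%.

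**The case against.** The strongest reply is that this is one stray bullet. Change from baseline is stated in the synopsis endpoint row, 3.1, 10.4 and 11.2, and section 10.2 promises a detailed SAP for each trial in a separate document. This stands. A reader might infer that the depression trial has two competing primary analyses, or that the sponsor could choose between them after seeing the data. Free choice would be costly. With equal SDs the two test statistics have correlation √((1 − ρ)/2) under the null, and rejecting on either one at 0.049 gives a two-sided error of 8.6% to 9.2% for ρ from 0.3 to 0.7. But the documents do not support that reading, because the endpoint definition and the full analysis section both fix the variable as change.

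A reader might also infer that the 10.4 analysis is underpowered. That is not shown either. If 10 is the SD of the change, 10.4 has exactly the stated power. Section 10.1 speaks of a 4-point and a 2.8-point change, which is at least compatible with that meaning. If 10 is the SD of a score, power falls below 90% only when ρ is below 0.5 (with equal SDs).

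Finally, a change-score t-test is valid under randomisation, so baseline adjustment is an improvement and not the correction of an error. It would replace the method in 10.4, whereas correcting the bullet only reconciles the text. This also stands, and the two are kept apart in the fix.

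**Conclusion.** The contradiction is real and lies in current text. The synopsis bullet misstates the primary test; 10.4, with the endpoint definitions behind it, is the plan. The practical effect is that a reader of the synopsis would expect a different test, whose estimate departs from that of 10.4 by the chance baseline difference (standard error 0.86 points if the baseline SD is 10).

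The second, separate gap is that 10.1 does not identify its SD. Depending on its meaning, the stated 90% is either exact for the 10.4 test or stands in for anything from about 78% to 99%. These ranges rest on the assumed correlations of 0.3 to 0.7 and on equal SDs. They show what is left open and do not demonstrate a shortfall in power.

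**What to change.** 1. **Synopsis, Statistical Analyses, depression bullet:** replace the 3-month score with the change in T-score from baseline to 3 months, as in 3.1 and 10.4. Carry the same single definition into the separate depression SAP. This costs wording only.

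2. **Section 10.1, depression:** state whether the SD of 10 is for the score or for the change, and give the assumed correlation with its source. If it is the score SD, show the resulting power of the 10.4 test. This costs a sentence and a short calculation.

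3. **Recommended improvement, section 10.4:** make the primary model the 3-month T-score adjusted for baseline T-score and the pediatric/adult stratum. Using change as the outcome in that model gives the same treatment estimate. Handle site parsimoniously (for example as a random effect), because the synopsis anticipates 60-80 clinics and a separate term for each would be wasteful. With equal SDs and correlations of 0.3 to 0.7, baseline adjustment gives 92.5% to 99.5% power if 10 is the score SD and 98.1% to 94.1% if it is the SD of the change. These figures model baseline only, not stratum or site. No new data are needed, since baseline T-scores are already collected. It does change the primary method, so it needs an amendment fixed before any unblinded comparison of outcomes.

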2. INTRODUCTION

2.1 Background, Significance, and Rationale

Study Rationale

Pain and depression are conditions that impact substantial proportions of the US population. Finding safe and effective drug therapies for both conditions is challenging. In the case of treatment for acute and chronic pain, the challenge is finding effective therapy while minimizing adverse effects or opioid addiction (and the ensuing consequences). For depression, there are few clinically relevant predictors of successful treatment leading to multiple trials of inadequate therapy for some patients. Both opioid and antidepressant prescriptions can be guided by pharmacogenetics (PGx) data based on existing guidelines from the Clinical Pharmacogenetics Implementation Consortium (CPIC). A pilot study conducted during IGNITE-1, in patients with chronic pain supports the potential benefit of a genotype-guided approach to pain therapy.[1] Existing studies of tailored antidepressant therapy are small and often industry-sponsored but suggest the genotype-guided approach is superior to usual care. We propose a randomized pragmatic clinical trial that enrolls patients into three PGx-guided therapy scenarios: acute post-surgical pain, chronic pain, and depression. For each scenario, participants will be randomized to genotype-guided drug therapy versus usual approaches to drug therapy selection (hereafter referred to as usual care). Changes in patient reported outcomes representing pain and depression control using standard PROMIS scales define the primary endpoints. Secondary analyses include safety endpoints, changes in overall well-being, and economic impact represented by differences in healthcare utilization and cost effectiveness.

Background and Significance

Acute and chronic pain represents the most prevalent and expensive public health condition in the U.S., affecting an estimated 100M Americans with annual costs to society estimated at \$635B dollars.[2, 3] This exceeds the combined costs of cancer, AIDS and heart disease.[3] Opioids have become a mainstay of treatment for chronic pain, yet analgesic responses to opioids are widely variable in both acute and chronic pain.[4, 5] Opioid prescribing rates have more than tripled since 1999, with 65 in 100 people getting an opioid prescription in 2016, and nearly 215M opioid prescriptions dispensed.[6, 7] Nearly half of all opioid prescriptions originate in primary care, and approximately 35% are from surgeons.[8]

Tramadol, codeine, hydrocodone, and oxycodone comprise the vast majority of opioids prescribed in the U.S.[9] Codeine and tramadol are dependent on bioactivation by the CYP2D6 enzyme to morphine and O-desmethyltramadol, respectively, which have 200-fold greater affinity for the μ -opioid receptor than their parent compounds. CYP2D6 genotype has important relevance for response to codeine and tramadol. Specifically, 5-10% of individuals are poor metabolizers (PMs), with no active CYP2D6 enzyme secondary to frameshift mutations (*3, *6), splicing defects (*4), or complete gene deletion (*5). As a result, PMs are unable to generate the active metabolites of codeine and tramadol and may derive no pain relief from these drugs.[10] Another 2-11% are intermediate metabolizers (IMs), with significantly impaired enzyme activity secondary to having both a nonfunctional and a reduced function CYP2D6 allele and may derive little pain relief from codeine and tramadol. At the opposite extreme, approximately 1-2% of individuals are ultra-rapid metabolizers (UMs) with CYP2D6 gene duplication/multiplication. UMs are at increased risk for toxic concentrations of active opioid metabolites, with reports of life-threatening toxicity and death with codeine or tramadol.[11-15] Hydrocodone and oxycodone undergo similar metabolism via CYP2D6 to compounds with 10- to 40-fold higher receptor affinity, respectively, and recent data support CYP2D6 genotype as an important contributor to hydrocodone efficacy, though risk exists for both drugs in those with UM phenotypes.[1]

Guidelines support *CYP2D6* genotype-guided use of opioid analgesics, but this is rarely done in clinical practice.[10] In a single center PCT[1], *CYP2D6* genotype-guided prescribing led to improved pain control in PMs and IMs compared to a traditional pain management approach. We now propose a multi-center PCT in which we will make recommendations based on *CYP2D6* genotype and *CYP2D6* enzyme inhibitor drug interactions that can convert individuals to PM or IM phenotypes. In PM, IM and UM we will recommend avoidance of hydrocodone, tramadol and codeine, and for normal metabolizers (NM), tramadol will be recommended as the preferred opioid, given its opioid and non-opioid mechanisms and purported lower risk for misuse.[16, 17] One study suggested the potential for abuse and dependence with tramadol in patients with chronic non-cancer pain was significantly less than for hydrocodone, and not different from that of non-opioid analgesics.[16]

The prevalence of major depressive disorder ranges from 5 to 10% in primary care, and it can be as high as 37% after critical care hospitalizations and surgeries.[18] SSRI prescriptions have increased 5.8-fold between 1991 and 2011.[19] Response to SSRIs and other antidepressants depends on numerous factors, but pharmacokinetic adjustments based on drug-drug interactions, renal and hepatic function, and pharmacogenomic variants within *CYP2D6* and *CYP2C19* play a substantial role in interindividual drug response.[20]

Existing clinical trials of PGx-guided treatment of depression have been primarily industry-sponsored and often investigate proprietary treatment algorithms.[21] One open label, non-randomized study demonstrated significantly improved depression outcomes in 227 adults with major depressive disorder (MDD) treated with PGx-guided prescribing of psychotropic medications relative to unguided participants.[22] Another 12-week randomized, double-blind trial of 144 adults with MDD receiving PGx-guided prescribing reported a 2.52-fold greater chance of remission of depressive symptoms. A randomized clinical trial of 685 adults with anxiety and depression identified significantly improved outcomes relative to controls in patients diagnosed with depression or anxiety using pharmacogenetic-guided medication selection.[23] A meta-analysis of randomized controlled trials of pharmacogenetic tests and depressive symptom remission concluded that individuals receiving treatment of depression with pharmacogenetic-guided decision support tools were 1.71 (95% CI: 1.17-2.48; $p = 0.005$) times more likely to achieve symptom remission relative to individuals who receive treatment as usual.[24] Another industry-sponsored, randomized, double-blind prospective trial with only 51 study subjects (26 pharmacogenetic-guided versus 25 unguided) reported a trend toward improved clinical outcomes in a 10-week trial. PGx-guided participants with depression had greater than double the likelihood of response and remission. Mean percent improvement in depressive symptoms was higher for the PGx-guided group over Treatment as Usual (TAU). PGx-guided treatment doubled the likelihood of response in patients with treatment resistant depression.[25] A more recent double-blind randomized controlled trial of 316 adults with MDD failed to report a difference in sustained response within a 12-week period. However, the PGx-guided treatment group had a higher responder rate compared to treatment as usual.[26]

While the above clinical trials suggest improved depression outcomes with use of pharmacogenomic-guided management of psychotropic medications when treating major depression in outpatient psychiatric practices, the majority of the trials were small and sponsored by industry. Importantly, a large, definitive trial with non-proprietary drug selection algorithms has not yet been published. Three of the six most commonly used SSRIs (sertraline, citalopram, and escitalopram) require functional *CYP2C19* enzyme activity for their hepatic inactivation *in vivo*, and CPIC recommends dose reduction in the setting of a *CYP2C19* poor metabolizer phenotype (to reduce probability of side effects) and alternative drug in the setting of a *CYP2C19* ultra-rapid or rapid phenotype (to reduce the probability of pharmacotherapy failure).[27] Two additional common antidepressants (fluvoxamine, paroxetine) are oxidized by *CYP2D6*, one of the most polymorphic of all human enzymes. For the present investigation,

PGx-guided antidepressant selection will follow CPIC guidelines for *CYP2D6* and *CYP2C19* phenotypes with regard to the selection or dosing of antidepressants.

